#### **6. SAFETY & EVENT REPORTING**

## 6.1 ADVERSE EVENTS

An AE is any untoward sign, symptom or medical condition occurring at any time after the subject receives his/her first dose of study drug, even if the event is not considered to be related to the study drug. Information about all AEs whether volunteered by the subject, discovered by Investigator questioning, or detected through physical examination, laboratory test, or other means, will be collected, and recorded on the AE CRF and followed as appropriate.

Abnormal laboratory values or test results constitute AEs only if they induce clinical signs or symptoms, and are considered clinically significant, or require therapy. They will be recorded on the AE CRF under signs, symptoms, or diagnosis associated with them.

As far as possible, each AE will be described by:

- Its duration (start and end dates)
- The severity grade (mild, moderate, severe)
- Its relationship to the study drug (suspected/not suspected)
- The action (s) taken and as relevant
- The outcome

Criteria for determining the severity of an AE and its relationship to the study drug are shown below in Table 5-1. These criteria are guidelines. It is the responsibility of the Investigator to decide of severity and whether or not a relationship to study drug is suspected.

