### b. Secondary Objectives

1. To measure the distribution of inspiratory flow rates with an InCheck Dial device set on measuring PIF using the medium low resistance setting in patients admitted with COPD exacerbations at Baylor University Medical Center, Dallas TX at the time of enrollment and day of discharge.
2. To determine the hospital length of stay for patients admitted with the diagnosis of COPD exacerbation.
3. To monitor and report any side effects from using once-daily ICS/LABA/LAMA or PRN therapy.
4. To evaluate the transition of care in delivering respiratory therapy medications from hospital to home.
5. To compare the number of PRN treatments, length of hospital stay, and rate of readmissions with findings in a previously analyzed historical cohort of 60 patients in our healthcare system.

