**Table 1 Adverse Event Severity and Relationship to Study Drug**

AE Severity	
Mild	Awareness of sign or symptom but easily tolerated

Moderate	Discomfort sufficient to cause interference with normal activities
Severe	Incapacitating, with inability to perform normal activities
AE Relationship	
Suspected	A clinical event, including laboratory test abnormality, with a reasonable time sequence to drug administration, which might or might not be also explained by concurrent disease or other drugs or chemicals
Not Suspected	A clinical event, including laboratory test abnormality, judged to be clearly and incontrovertibly due to extraneous causes (diseases, environment, etc.), or with a temporal relationship to drug administration which makes a causal relationship improbable, and/or for which other drugs, chemicals or underlying disease provide a much more plausible explanation

Adverse events (including serious adverse events) will be monitored and reported from enrollment to discharge.

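### Secondary objective 3 covers side effects of TRELEGY or PRN therapy, but each adverse event is judged for relationship to TRELEGY only, so suspected PRN albuterol effects are not identified

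*Combined protocol and SAP*

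**What the plan says.** Section 2.b, repeated in the synopsis, gives secondary objective 3 as "To monitor and report any side effects from using once-daily ICS/LABA/LAMA or PRN therapy". Section 5.2.4 defines the PRN treatment as nebulized albuterol 2.5 mg, given as needed from enrollment to discharge.

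Section 6.1 lists how each AE is described. The list includes "Its duration (start and end dates"), severity, action taken and outcome. It has one causality item, "Its relationship to the study drug (suspected/not suspected"). The duty placed on the investigator is equally narrow: "It is the responsibility of the Investigator to decide of severity and whether or not a relationship to study drug is suspected".

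Table 1 defines the two codes. A *Suspected* event is one with a reasonable time sequence to drug administration, "which might or might not be also explained by concurrent disease or other drugs or chemicals". A *Not Suspected* event is one "judged to be clearly and incontrovertibly due to extraneous causes (diseases, environment, etc".), or one whose timing makes a causal link improbable, and/or one "for which other drugs, chemicals or underlying disease provide a much more plausible explanation".

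On timing, Section 6.1 counts an event as an AE only after the first dose of study drug. The sentence after Table 1 says: "Adverse events (including serious adverse events) will be monitored and reported from enrollment to discharge".

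**The concern.** A side effect is an event attributed to a treatment. The objective asks for side effects of two treatments, while the plan collects an attribution for one. Followed as written, no AE is marked at the time it occurs as a suspected effect of PRN albuterol. The PRN half of objective 3 would then rest on an unplanned look back through the records.

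Confusion between the two drugs is easy to foresee. TRELEGY contains vilanterol, a long-acting beta agonist, and albuterol is a short-acting one, so some effects could come from either drug or from both. The start of the AE definition adds a smaller gap: albuterol may be given under the protocol before the first TRELEGY dose.

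**Working it through.** No statistical calculation applies. The check sets the sections side by side.

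**1. What *study drug* means.** Section 6.3 describes the study drug as the product given through the ELLIPTA device, and albuterol is nebulized (Section 5.2.4). Section 15 treats all care apart from the study drug as routine. So the causality item in Section 6.1 refers to TRELEGY and does not reach albuterol.

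**2. Whether another section fills the gap.** Section 6.2 (serious events), 7.1 (concomitant medication), 8.1 (safety measurement), 8.7 (statistics) and 12 (safety monitoring) contain no item on relationship to albuterol or PRN therapy. The objective names 2 therapies, and 1 has a causality item.

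**3. What the codes can show.** Classify each event by the drug or drugs the investigator suspects. Two yes/no judgements give 2 × 2 = 4 possible answers. One yes/no judgement gives 2 codes.

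| Investigator suspects | Code under Table 1 | With a second item for albuterol |
|---|---|---|
| TRELEGY only | Suspected | TRELEGY yes, albuterol no |
| Both | Suspected | TRELEGY yes, albuterol yes |
| Albuterol only | Not Suspected | TRELEGY no, albuterol yes |
| Neither | Not Suspected | TRELEGY no, albuterol no |

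The events in which albuterol is suspected are rows 2 and 3. Under Table 1 they are split across the two codes, and in each code they are mixed with events in which albuterol is not suspected.

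**4. What can be recovered later.** Section 5.2.4 collects the number and time of albuterol treatments daily, when available. Section 7.1 collects concomitant medication, and Section 16.2 requires source documents. Section 6.1 asks for AE dates and not for onset times. TRELEGY is given every day, so on a day with a PRN treatment the date does not separate the drugs. Even a recorded onset time would help only a little, because an event after the first dose follows exposure to TRELEGY in any case.

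**5. The start of the AE definition.** Section 5.2.4 starts TRELEGY on the morning of enrollment if feasible, otherwise the next morning, with dosing between 06:00 and 12:00. A patient enrolled at 12:00 and first dosed the next day waits 18 hours (12:00 to 06:00) to 24 hours (12:00 to 12:00). PRN albuterol is available in that interval. An albuterol effect in it is inside the monitoring period stated after Table 1 and outside the definition in Section 6.1.

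**The case against.** The best defence is that objective 3 promises no split by drug. It can be read as the safety of the whole regimen. All AEs are recorded whether or not they are related, followed to discharge and summarized descriptively (Sections 6.1, 8.1 and 9). Section 6.1 also records the action taken, which could show that albuterol was withheld or changed. No planned test or stopping decision uses attribution by drug. For shared beta-agonist effects, a second item will often be ticked for both drugs.

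Much of this stands, and it keeps the point small. It does not remove it. The objective names PRN therapy as a source of side effects in its own right, and a list of all AEs does not say which ones the investigator suspected were due to it. Action taken is a clue and not a causality judgement.

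Two stronger readings are tempting, and the documents do not support them. First, a reader might infer from the *Suspected* definition, which allows other drugs as a further explanation, that albuterol-only events will be charged to TRELEGY. An event that the investigator attributes to albuterol alone is by that judgement not suspected for TRELEGY, and Table 1 sends it to *Not Suspected*. If TRELEGY is still suspected, the event belongs to both drugs. The fault is missing identification, and inflation of the TRELEGY count is not shown. Second, a reader might infer that objective 3 requires four attribution groups. It does not say so. The four rows above are what two yes/no items produce and are a convenient way to report.

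**Conclusion.** The mismatch is real and is confined to the protocol text. Section 6.1 and Table 1 do not identify suspected PRN albuterol effects, although objective 3 asks for side effects of PRN therapy to be reported. The AE definition also starts later than the stated monitoring period. A reader might infer that monitoring from enrollment already covers all PRN use, but Section 6.1 excludes events before the first TRELEGY dose.

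Severity is minor. The primary endpoint, sample size, treatment and planned tests are unaffected. The documents give no AE rate, so the number of events involved is unknown. The conclusion rests on reading *study drug* as TRELEGY, which Sections 6.3 and 15 support, and on the protocol wording alone. The AE form is not in the documents and may already hold such an item. This is a cheap improvement and not a flaw that threatens the study's conclusions.

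**What to change.** - In Section 6.1, Table 1 and the AE form, add relationship to PRN albuterol (suspected/not suspected), judged separately from relationship to TRELEGY.
- Start the AE definition at enrollment, to agree with the sentence after Table 1.
- Report AEs and serious AEs descriptively, as counts and percentages by suspected drug: TRELEGY, PRN albuterol, both, neither.
- For any patients already enrolled, assign albuterol causality from source notes and logged treatment times, and flag it as retrospective.
- Onset time is optional. It is of limited value because TRELEGY is given daily.

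The cost is one extra item on the AE form, a written amendment under Section 16.1 with IRB review, and some retrospective coding. No extra visit is needed. The item will not separate the drugs where their effects overlap, but it will put on record which drugs the investigator suspected.

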**Table 1 Adverse Event Severity and Relationship to Study Drug**

AE Severity	
Mild	Awareness of sign or symptom but easily tolerated

Moderate	Discomfort sufficient to cause interference with normal activities
Severe	Incapacitating, with inability to perform normal activities
AE Relationship	
Suspected	A clinical event, including laboratory test abnormality, with a reasonable time sequence to drug administration, which might or might not be also explained by concurrent disease or other drugs or chemicals
Not Suspected	A clinical event, including laboratory test abnormality, judged to be clearly and incontrovertibly due to extraneous causes (diseases, environment, etc.), or with a temporal relationship to drug administration which makes a causal relationship improbable, and/or for which other drugs, chemicals or underlying disease provide a much more plausible explanation

Adverse events (including serious adverse events) will be monitored and reported from enrollment to discharge.

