#### **5.2.4 TREATMENT (Enrollment to Discharge)**

TRELEGY ELLIPTA (fluticasone furoate 100 mcg, umeclidinium 62.5 mcg, and vilanterol 25 mcg inhalation powder) will be initiated on the morning of enrollment if feasible, or the morning after enrollment otherwise. Treatment will continue daily until discharge. Treatments will be administered by a respiratory therapist daily in the morning between 06:00 AM and 12:00 PM. Patients will receive nebulized short-acting beta-2 agonist (SABA) treatments of albuterol sulfate (2.5mg) as needed during hospitalization. Patients will receive prednisone 40 mg PO daily for the first 7 days from enrollment, subtracting 1 day for each consecutive day the patient received systemic corticosteroid treatment prior to enrollment.

Treatment procedures/assessments include:

- Concomitant Medications
- AE Assessment
- TRELEGY administration

Data from the following specified assessments will be collected daily, when available, and entered the case report forms (CRFs):

- Vital Signs
- Short-acting beta agonist (SABA) therapy: number and time of treatments

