#### **5.2.5 DISCHARGE**

Upon discharge, patients will receive a full TRELEGY ELLIPTA inhaler containing 30 doses with instructions to take 1 puff daily in the morning for 30 days. The in-hospital use TRELEGY ELLIPTA used by the patient will be discarded.

The following procedures/assessments will be done prior to hospital discharge:

- Spirometry (FEV1, FVC, FEV1/FVC)
- Peak inspiratory flow rate, measured by the InCheck Dial set at medium resistance.
- Concomitant Medications
- Adverse Events (AE) Assessment
- Patient Satisfaction Questionnaire (St George's Respiratory questionnaire, short version)

In addition, data from the specified assessments will be collected when available, and entered the case report forms (CRFS):

- Vital signs
- Withdrawal from protocol

If for any reason, some of the research assessments at discharge are not performed, the study team may (at investigator's discretion) schedule a follow-up with the subject in the research clinic to obtain the missed assessments.

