#### **5.2.6 30 DAY POST DISCHARGE/WITHDRAWAL FOLLOW-UP**

Subjects will receive a follow-up phone call from a study coordinator and Medical Charts will be reviewed to assess if the subject was readmitted within 30 days of discharge. Follow-up phone call and Medical Chart review will instead occur 30 days after withdrawal for patients who are withdrawn prior to discharge.

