## 6.2 SERIOUS ADVERSE EVENTS

All Serious Adverse Events (SAEs) will be reported to the sponsor within 24 hours of awareness of the event. An AE will be considered serious if it meets any of the following criteria:

- Events resulting in death.
- Life-threatening events
- Events requiring hospitalization or prolongation of existing hospitalization.
- Events resulting in persistent or significant disability/incapacity.

- Events not meeting any of the above criteria deemed to be serious by the Investigator.

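### AE and SAE collection ends at discharge, but patients go home with 30 days of study drug, so most exposure and every 30-day readmission fall outside safety reporting

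*Combined protocol and SAP*

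**What the plan says.** The text after Table 1 in section 6.1 sets the window: "Adverse events (including serious adverse events) will be monitored and reported from enrollment to discharge". The visit sections agree with it. AE assessment is listed at enrollment (5.2.3), during treatment (5.2.4) and at discharge (5.2.5), but not at the 30-day contact (5.2.6). Concomitant medication recording also stops at discharge (7.1).

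Study treatment does not stop there. Section 5.2.4 covers the hospital stay ("Treatment will continue daily until discharge"), and section 5.2.5 adds the home supply: "patients will receive a full TRELEGY ELLIPTA inhaler containing 30 doses with instructions to take 1 puff daily in the morning for 30 days". Section 8.2 makes adherence to that supply an endpoint, and section 5.1 follows patients to 30 days after discharge.

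At 30 days, section 5.2.6 provides a contact: "Subjects will receive a follow-up phone call from a study coordinator and Medical Charts will be reviewed". Its stated purpose there is readmission, and section 8.2 adds home compliance.

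Other text has no end date. Section 6.1 defines an AE as an event "occurring at any time after the subject receives his/her first dose of study drug". Section 6.2 requires SAEs to reach the sponsor within 24 hours of awareness, and its criteria include death and "Events requiring hospitalization or prolongation of existing hospitalization". Section 6.5 collects pregnancies up to a safety follow-up visit that sections 5.2.1 to 5.2.6 do not describe. Secondary objective 3 reads: "To monitor and report any side effects from using once-daily ICS/LABA/LAMA or PRN therapy".

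**The concern.** The drug under study is taken for longer at home than in hospital, but side effects are sought only in hospital. Section 14.2.1 lists pneumonia and oral candidiasis among the common reactions in COPD. If either arises at home and does not lead to readmission or death, no planned procedure would record it. An AE table built from this window would look like the safety profile of the whole regimen but would describe only its first few days.

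Serious events raise a second problem. An unplanned readmission for illness while on study drug meets the criteria in section 6.2, as does a death. The plan counts both as efficacy outcomes (sections 2d, 8.2 and 8.7). Under the section 6.1 window, neither requires an AE record, a causality judgement or a timed report to the sponsor. Section 13 dispenses with a monitoring board, so AE and SAE reporting is the main safety mechanism the study has.

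Third, staff who learn of a serious event on day 10 at home cannot tell from the protocol whether it is reportable: section 6.2 says yes and the sentence after Table 1 says no.

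**Working it through.** The plan states no figure to reproduce. The check has two parts: how much exposure lies outside the window, and which events do.

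**Inputs from the protocol**
- AE/SAE window: enrollment to discharge (6.1).
- Inpatient dosing: one dose a day until discharge (5.2.4).
- Home supply: 30 doses, one a day (5.2.5).
- Planned enrollment 80, with 30-day follow-up expected in 80% (4a): 80 × 0.80 = 64.

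**Assumptions, because the protocol gives no values**
- L, the number of inpatient doses: 2 to 14.
- c, the fraction of home doses taken: 0.5 to 1.
- 30-day readmission rate: 15% to 25%, for illustration only.

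**Share of doses taken after the window closes** = 30c / (30c + L)

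| L | c = 1 | c = 0.8 | c = 0.5 |
|---|---|---|---|
| 2 | 93.8% | 92.3% | 88.2% |
| 3 | 90.9% | 88.9% | 83.3% |
| 5 | 85.7% | 82.8% | 75.0% |
| 7 | 81.1% | 77.4% | 68.2% |
| 10 | 75.0% | 70.6% | 60.0% |
| 14 | 68.2% | 63.2% | 51.7% |

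For example, with L = 5 and c = 1: 30 / 35 = 85.7%. The share falls to one half only when L = 30c, that is at 30, 24 or 15 inpatient doses for c = 1, 0.8 or 0.5.

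**Patient-days gained by extending the window.** All patients followed: 80 × 30 = 2,400. At 80% follow-up: 64 × 30 = 1,920. With L = 5 the present window covers 80 × 5 = 400 patient-days. The extended window would cover 400 + 2,400 = 2,800, or 400 + 1,920 = 2,320 at 80% follow-up. Patients withdrawn before discharge would lower these totals.

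**Readmissions.** Section 5.2.6 counts them from discharge ("Medical Charts will be reviewed to assess if the subject was readmitted within 30 days of discharge"), so 100% occur after the window closes, whatever the rate. If 15% to 25% of patients were readmitted, that would be 80 × 0.15 = 12 to 80 × 0.25 = 20 patients. At 80% follow-up, 64 × 0.15 = 9.6 to 64 × 0.25 = 16 would be observed, or about 10 to 16.

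**What is captured after discharge under the plan as written**

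| Event at home | Recorded? | Handled as a safety event? |
|---|---|---|
| Readmission | Yes, as an efficacy outcome | Not under the 6.1 window |
| Death | Yes, through 30-day survival | Not under the 6.1 window |
| AE without readmission or death | No planned collection | No |

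**The case against.** The strongest reply is that the most serious events are not lost. Readmission and survival to 30 days are endpoints, found by phone and chart review. That is correct. What is missing for them is the safety handling. The events with no planned collection at all are those at home that lead to neither readmission nor death.

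A second reply is that section 6.2 has no end date, and section 6.1 says all AEs are collected, including those the subject volunteers. The 24-hour rule could therefore be read as continuing after discharge. That reading is possible, but it contradicts the sentence after Table 1, and no visit schedules the questions that would bring AEs to light. Either the window is too short or the text conflicts, and both need an amendment.

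Third, the cut-off may be deliberate: it is applied consistently to AE assessments and concomitant medication, in a single-arm phase IV study of an approved drug whose primary endpoint is in-hospital. The PRN half of secondary objective 3 is in fact covered, because nebulized albuterol is given only during the stay. But no rationale is offered, and the inhaler half of the objective is not covered. Section 13 uses approval to justify having no monitoring board, not to justify ending AE collection during dosing. Section 3b notes that this drug is seldom prescribed to hospitalized COPD patients.

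Three corrections of detail stand. A planned admission is not an untoward event, so the readmission count is not an SAE count. The readmission figures rest on an assumed rate. The pregnancy wording matters little in practice, because women of child-bearing potential are excluded.

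**Conclusion.** The concern holds. As written, AEs and SAEs are collected only for the inpatient part of a regimen that continues at home for 30 more doses. The home share of exposure is 81% to 94% for stays of 2 to 7 dosing days with full adherence. It remains above half (51.7%) with 14 inpatient doses and half the home doses taken. These shares depend on assumed lengths of stay and adherence, but the conclusion that most exposure is outside the window does not change anywhere in the range examined.

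That every 30-day readmission falls after the window needs no assumption. The count of 12 to 20 patients, or about 10 to 16 observed at the protocol's own follow-up rate, is illustrative, and the conclusion does not rest on it.

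The primary endpoint is unaffected. Secondary objective 3 cannot be answered for the inhaler beyond the hospital stay, and the reporting duty for serious events at home is contradictory. This should be corrected as a priority: mild events at home that are not asked about at the time may not be recoverable later.

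**What to change.** 1. **Section 6.1:** replace the sentence after Table 1 with one window that runs through the 30-day post-discharge contact, or the 30-day post-withdrawal contact for patients withdrawn before discharge. Fix the start as well. The AE definition begins at first dose and the present window at enrollment, and these can differ because dosing may begin the next morning. First dose would match the definition.
2. **Sections 5.2.6 and 7.1:** add AE, SAE and concomitant medication questions to the call and chart review that already take place. Medication data are needed to judge causality.
3. **Section 6.2:** state that deaths and unplanned readmissions in the window are reported as SAEs within 24 hours of awareness, with a causality assessment, as well as being counted as outcomes. Say how planned admissions are handled.
4. **Section 6.5:** name the contact that serves as the safety follow-up visit.
5. **Analysis:** report AEs separately for the inpatient and home periods, each with the number of patients assessed and the patient-days covered.

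No new visit is needed. The cost is an amendment to several short sections, with the approvals that sections 9.1 and 16.1 require, a longer call, and more AE and SAE forms. Some limits remain. A single call at day 30 relies on recall, may bring late awareness of serious events, and is expected to reach about 64 of 80 patients. The report should say so.
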